Real-world Evaluation of JBA GlucoTrojan with Reducose ® on Glycemic Response

NCT not assigned yet Date: July 8 2024

Real-world Evaluation of JBA GlucoTrojan with Reducose[®] on Glycemic Response

Summary

The project is focused on evaluating the real-world efficacy of JBA GlucoTrojan, a powdered supplement sachet containing Reducose, a natural water extract of White Mulberry Leaf, which has been scientifically proven to reduce the absorption of sugars and carbs by up to 40%. The study aims to compare the effect of consuming GlucoTrojan with a meal (Test Meal) vs. having the meal alone (control) on the blood sugar response of 50 healthy adults, pre-diabetes, or non-insulin dependent diabetes, over a period of 14 days. It is expected that GlucoTrojan will reduce the incremental area under the curve and the peak for plasma glucose concentration over 120 minutes in normoglycemic adults when compared to the response to a control meal.

Sponsor: *AQP Pharmaceuticals, Inc.* Contract research organization: Tastermonial Inc Principal investigator (PI): [name]. Co-investigator: [name], CEO

About Tastermonial

Food and supplement brands use the Tastermonial Platform to substantiate metabolic health claims by collecting data-driven insight from members of the public in a cost-effective manner.

Tastermonial consists of scientists and engineers who are passionate about conducting citizen scientist studies to help companies and their partners examine the efficacy of their product(s) via continuous-glucose-monitors (CGMs) and other biofeedback data sources. The results generated from our real-world studies are used to substantiate claims, drive consumer trust and brand loyalty, guide product development decisions, and de-risk clinical trials.

Disclaimer:

Please note that although Tastermonial conducted their studies in a real-world scenario and collected trustworthy data, these experiments were not conducted in a controlled setting, such as a laboratory, and the information does not hold any formal research significance.

Background

AQP Pharmaceuticals, Inc. ("Company") developed a powdered supplement sachet that can be added to meals targeting consumers who follow carbohydrate-heavy Asian diets. The product is formulated with the

patented ingredient, "Reducose[®]", a natural water extract of novel White Mulberry Leaf that has been scientifically proven to reduce the absorption of sugars and other carbs by up to 40%. The effects have been confirmed previously via Randomized, Double-Blind, Controlled Trials (see Appendix I and II).

The Company is looking to conduct a real-world study of blood glucose responses to JBA GlucoTrojan (see specifications here) with a 5% concentration of Reducose[®]. The study will observe the real-world efficacy of GlucoTrojan when taken with high carbohydrate meals.

The Company wishes to use the collected data to showcase the comparative glycemic impact as well as testimonials from participants to build trust and loyalty with their customers.

Rationale

Reducing the health impact of dietary sugar intake is a public health priority. Mulberry leaf extract may reduce blood glucose responses following sugar intake by reducing gastrointestinal carbohydrate absorption via alpha-glucosidase inhibition activity of iminosugar constituents such as 1-deoxynojirimycin (DNJ). Mulberry leaf extracts are widely consumed in Asia for normalizing post-prandial blood glucose. Reducose has been tested in multiple clinical trials and lowers the postprandial glucose response by up to 40% (see Appendix).

Hypothesis

An appropriate dose of GlucoTrojan when co-administered with a complete meal will reduce the incremental area under the curve and the peak for plasma glucose concentration over 120 minutes in normoglycaemic adults when compared to the response to a control meal.

Study Objective

To compare the effect of consuming GlucoTrojan (mulberry-extract formula) with a meal (Test Meal) vs. having the meal alone (control) on the blood sugar response of 50 healthy (non-diabetes) adults, pre-diabetes or non-insulin dependent diabetes (Tester). Experiments will span 14 days.

Materials and Methods

Design

Testers will be given sachets of GlucoTrojan and standardized test meals. The experiment is conducted by logging foods on the Tastermonial app and syncing the continuous glucose data from the monitor into the

Tastermonial app. Participants use the Tastermonial mobile iOS app to log what, when, and how they ate the tested product. The participants are instructed not to make changes in their usual diet and physical exercise during the study period. Additionally, participants are asked to note any medications or activities that can impact their postprandial glucose readings. The app is also used to collect qualitative data.

During the study period, each tester will be wearing a continuous glucose monitor (CGM) from Abbott Freestyle Libre (Link) to actively track their postprandial glucose responses for each meal. The Freestyle Libre measures interstitial glucose levels throughout the day and gives back data in 15-minute intervals, transmitting the results via an NFC receiver in a smartphone. Sensor memory limitations require the device to be scanned every 8 hours. Of note, CGM devices measure interstitial glucose levels (glucose from the fluid in between cells) While interstitial glucose and blood/plasma glucose levels correlate highly, they do not precisely show the exact same reading and incur a lag of about 2-7 minutes (as reported by the manufacturer here). Medical diagnoses are not made from interstitial measurements.

Participants enrollment

A total of 50 individuals will be recruited via the Tastermonial database and ambassador network. A study-specific online pre-screener (see appendix III) will be used to preliminarily identify potential subjects for the study. Information and guidance will be made available electronically and via our Trial Manager. Participants can ask questions to our staff via email, telephone calls, and video meetings. The Tastermonial platform will be used to manage the HIPAA-compliant data collection process.

Written informed consent for inclusion will be obtained digitally from all subjects before enrollment (check for a separated document). Participants will then conduct the study at home.

The sequence of events for the participant is as follows:

- Eligibility pre-screening based on a self-declared answers to questionnaire filled electronically by participants

- Informed consent signing

- Issuance of a CGM 14-day prescription (Rx) to the participant for it to be filled and the CGM picked up at their local pharmacy

- Shipment of Tastermonial test box containing 2 portions of the standardized test meals, the test instruction postcard and 15 sachets of GlucoTrojan with a 5% concentration of Reducose[®]

- Participants follow the self-service onboarding guide and step-by-step test instructions by scanning the QR code on the postcard found inside the Tastermonial box

- Participants apply the CGM and wait 1 day before starting the test

- Participants start the protocol and follow day-by-day instructions for the next 13 days
- Participants are asked to complete the product feedback surveys.

Inclusion & Exclusion criteria

Inclusion criteria:

- Consent to study protocol
- BMI: 18.5 to 29.9 kg/m2

• 21 to 75 years old

Exclusion criteria:

- Physician-diagnosed T1D and insulin-dependent T2D
- Taking medications that modulate blood glucose response or control blood pressure other than Metformin
- An underlying health condition that warrants non-participation
- Individuals who are pregnant
- Any other dietary restrictions that prevent them from consuming study foods
- Unable to follow remote guidance via the Internet or smartphone
- Unable to follow controlled diet instructions
- Unable to use a CGM (Continuous Glucose Monitoring Devices)

Withdrawal or Discontinuation of Study Participation

Participants are entitled to withdraw from the study at any point. In addition, the principal investigator has the authority to remove a participant due to medical concerns or if the participant no longer fulfills the study's inclusion and exclusion criteria. It is the participant's responsibility to inform the study personnel if they believe they no longer meet the criteria while participating. The sponsor reserves the right to pause, delay, or terminate the study if necessary.

Timeline

From study kick-off to completion, the investigators anticipate that the entire study will take in total about 7-10 weeks depending on how fast feedback is provided. Inclusion and exclusion criteria of the study will influence the recruitment time. During the study, the investigators will support ad-hoc requests from the Company to review incoming test results, provide a prompt update, and provide marketing assets from the comparative results of individual testers per request.

Prior to commencing the creation of study material and the recruitment, the Company shall agree on the above elements of the study design. The company may work with Tastermonial to co-develop an additional testing guide to fulfill new hypotheses and collect more data.

The investigators anticipate the following timeline after the investigators agree on the test design and protocol:

- Creation of study material e.g. ICF, study questionnaires, pre-screeners, digital protocol, and onboarding materials: 1-2 weeks*
- Enrollment of participants: 2-3 weeks
- Conducting the study: 2 weeks
- Data analysis & Report: 2 weeks

Execution plan

The investigators will carry out a within-subject comparative, open label study on enrolled participants. The experimental protocol is as follows:

Day 1: Start wearing the CGM sensor and let it self-calibrate for 24 hours

Day 2: Consume 1 serving of Test Meal for breakfast. Log the meal in the Tastermonial app.

Day 3: Consume 1 serving of Test Meal with GlucoTrojan for breakfast. Log the meal in the Tastermonial app.

Days 4-8: Participants will be instructed to take GlucoTrojan twice per day. Once during their typical breakfast meal and once during their typical dinner meal. Each breakfast and dinner will be logged in the Tastermonial app.

Days 9-13: Participants will continue with their typical lives but continue to log meals — breakfast and dinner — in the Tastermonial app.

Day 14: The experiment ends

On Day 1 and Day 2, testers must avoid eating foods or drinking anything except water after 10 PM and until 6 AM. At the start of each test, the investigators will ask testers to confirm that their blood glucose is within the typical resting range (70-100 mg/dL). If their blood glucose is not within the resting range, the investigators will ask testers to wait and check again in 15 minutes before starting the experiment. The test meal must be consumed within 10 minutes.

General instructions that apply from Day 1 to Day 14:

- 2 hours before the required action, refrain from strenuous exercise
- 2 hours after the required action, avoid other foods and refrain from strenuous exercise
- Use the proprietary Tastermonial smartphone app to scan the barcode or manually log test products and meals to record the serving size as they start eating. All events outside of the instructed ones should be noted in the food log.
- The context for each experiment should be consistent. E.g., if black coffee or tea is consumed within 2 hours after the required action, it should be consistently consumed for all experiments.

Data Handling & Analysis

Data Collection

The entire 14-day historical blood glucose data from the participants will be made available for analysis. The 2-hour postprandial blood sugar readings within a 15-minute interval will be analyzed, as well as the time-in-range of participants.

Additional demographic profiles of participants will be collected and analyzed, including clinical parameters (age, sex, body weight, height, body mass index, meal composition; i.e.,calories, carbohydrates, fats, proteins, and fiber) and individual resting glucose range (Baseline Glucose Range) to determine their glycemic cohort.

The investigators will also collect qualitative data. Participants will be asked to report their feelings such as mood and well-being during and after the experiments in an online questionnaire. The questionnaire will be finalized with the approval of the company.

Data management

All documents relevant to the study, including completed ICFs, are hosted on a secure online portal. The ICFs are completed using a secured data transfer system on the HIPAA-compliant online portal. The company has access to the de-identified data set. The data is saved to a secured internal network. All data is anonymized during the analysis. HIPAA relevant PHI data privacy of participants is ensured on a secured online portal that uses the HIPAA compliant AWS servers. All participants are de-identified and labeled using a coding system.

Test Validation Methods

To ensure that the test was conducted under ideal conditions, e.g. on an empty stomach, the investigators rely on the participant's computed "baseline" or resting glucose average value, calculated as the average of all their glucose values from 1 AM to 4 AM each morning over the lifetime of the sensor. If the test was started far above the individual's **baseline range**, the test is considered an outlier and excluded from our initial analysis. This methodology was reviewed by a registered dietitian and a statistician.

The Baseline range

The baseline range of each individual is computed between 1 AM to 4 AM each morning over the lifetime of the sensor.

Several studies performed specifically using continuous glucose monitors suggest that a non-diabetic, healthy individual can expect:

- Maximum baseline range should not exceed 102 mg/dl for average non-diabetic testers
- ✤ Mean post-meal glucose peaks ranging from 99.2 ± 10.5 to 137.2 ± 21.1 mg/dl
- Time to post-meal glucose peak is around 46 minutes 1 hour
- Fasting glucose levels between 80-86 mg/dl

These are not standardized criteria or ranges but can serve as a simple guide for what has been observed as normal in individuals without diabetes.

iAUC Calculation

Each participant's eating period (called a "meal") is normalized and overlaid in a data frame that captures glucose values over the course of the test. Several other metrics are computed, such as maximum and minimum values, standard deviation, and others. In particular, the investigators compute the iAUC ("incremental area under the curve"), a measure of the total amount of postprandial blood glucose level increased over the entire 2-hour period after eating. The methodology of iAUC calculation follows the gold standard used in the measurement of the glycemic index. The iAUC metric allows our team to easily compare and rank testing results, as well as compare against the pure sugar responses or the sugar tolerance test of an individual.

Data from each user is analyzed by our team and verified by a practitioner and a statistician. The raw Libreview data is annotated by the timestamps and the food log generated through the Tastermonial app.

Summary of obtained data

- A Glycemic Impact Exploratory Data Exports file in .xlsx/.csv format:
 - Anonymized blood glucose analysis including time-in-range
 - Per individual
 - Per experiment log
 - Metrics including iAUC, time to peak, peak (mg/dl), indicative GI & GL
 - Anonymized food log data
 - Anonymized tester profile and demographics data
 - Statistical Significance Analysis P-Value, Mean, Std Deviation at 95% confidence level

An example is shown below:

Limitations of the study and disclaimer

The investigators suggest the Company to not draw any final conclusion from the statistical analysis illustrated above, given the nature of this real-world observational study. A notable advantage of using this system is that volunteers are tested in real-world conditions. However, the test subjects were not under strict research testing conditions which could have caused a variance in the data generated. Further studies are required to further confirm our findings. As opposed to the randomized control trial studies, the collected data should provide a basis to further observe the different use cases, contexts and the customer profiles that the Company can market to.

Categorization of Study Risk and Dietary Supplement Safety

The study falls under the "Minimal Risk" category, as the dietary supplement ingredients selected for the study have been well-tolerated in previous clinical studies and consumer products. These ingredients have either been on the market or submitted as new dietary ingredients to the FDA. The manufacturing process

used to obtain the extracts from the appropriate plant sources did not cause any chemical alterations. Moreover, the selected dietary supplements have a high safety profile, and the daily doses are within the upper limits tolerated by the FDA (where applicable). The ingredients are also on the GRAS list, and although there is a possibility that some participants may have a sensitivity to the herbal ingredients, there are no known side effects associated with the test product. The potential benefits of the dietary supplements outweigh the negligible risks, except for the potential risk of gastrointestinal upset for participants with previously unrecognized allergies or sensitivities to any ingredient. Regarding confidentiality, the risk is minimal as all study participant information will be de-identified, and since it is a virtual study, no confidential or protected information will be taken outside the standard. In the unlikely event that complications arise, and additional medical care is required, there is a slight financial risk to the participants.

Assessment of Benefits

This study aims to evaluate the benefits of using the test product, including enhancements in participants' quality of life and improvements in their blood glucose levels.

Conflict of interests

Ensuring the impartiality of this study, free from any actual or perceived external influence, is of utmost importance. To that end, any individual involved in the trial's design, implementation, analysis, publication, or any other aspect must disclose and appropriately manage any actual or perceived conflict of interest. In cases where a perceived conflict of interest exists, the individual must take measures to ensure their involvement in the trial is conducted appropriately.

Given that the sponsor will benefit financially from the study's success, it is imperative to manage their conflict of interest. To achieve this, an independent PI will oversee the study's execution, and Tastermonial will handle all aspects related to the design, administration of participant-focused materials, participant recruitment, and data collection.

Payment

Participants will get a \$20 gift card to use for future Tastermonial purchases.

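### No eligibility criterion keeps people with a commercial tie to the CRO or sponsor from being testers, although recruitment runs through the CRO's undefined ambassador network and the study is open label at home

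*Protocol*

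**What the plan says.** Under Participants enrollment the protocol names two recruitment sources, both belonging to the CRO: "A total of 50 individuals will be recruited via the Tastermonial database and ambassador network". The word ambassador is not explained, and no split between the two sources is given. Eligibility is established by "Eligibility pre-screening based on a self-declared answers to questionnaire filled electronically by participants". Only the heading of that questionnaire (Appendix III) is available.

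The Inclusion & Exclusion criteria list three inclusion and eight exclusion items. They cover consent, BMI, age, health, medication, pregnancy, diet and ability to carry out the procedures, for example "Unable to follow remote guidance via the Internet or smartphone".

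On design, the Execution plan says: "The investigators will carry out a within-subject comparative, open label study on enrolled participants". The order is fixed, with the control meal on Day 2 and the same meal with product on Day 3. On setting, Participants enrollment says: "Participants will then conduct the study at home".

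The Conflict of interests section opens with "Ensuring the impartiality of this study, free from any actual or perceived external influence, is of utmost importance". It asks everyone involved in the trial to disclose and manage conflicts. Against the sponsor's financial interest it sets an independent principal investigator and the arrangement that "Tastermonial will handle all aspects related to the design, administration of participant-focused materials, participant recruitment, and data collection".

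**The concern.** The protocol gives impartiality high priority, but its named safeguards are directed at the sponsor. Handing recruitment to the CRO does nothing about testers who are tied to the CRO, and one of the two recruitment routes is a network of people associated with it.

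A tester with a stake in the platform or the product could, without meaning to, run the product day more favourably than the control day. The within-subject comparison removes stable differences between people. It does not remove conduct that differs between two days the tester can tell apart.

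Tester output also has a commercial use. The Background section plans to use participants' testimonials, and the Timeline section offers marketing material built from individual testers' results. A testimonial from a tied person presented as an ordinary participant's would be a credibility problem whatever the effect on iAUC. The mood, well-being and product feedback data are the most exposed, because they are wholly self-reported.

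**Working it through.** The protocol has no figure to reproduce here: it gives no share of ambassadors and no assumed effect or variance. The check is a reading of the criteria and of who performs each step.

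**1. Criteria.** Of 3 inclusion items, 0 concern a commercial, employment or family tie. Of 8 exclusion items, 0 do.

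**2. Can a disclosed tie be acted on?** The disclosure duty under Conflict of interests is worded broadly enough that it might reach testers. However, no step in the participant sequence collects such a disclosure. The section on withdrawal gives the principal investigator two grounds for removing a participant: medical concerns, or no longer meeting the criteria. As no criterion covers a tie, neither ground applies.

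**3. Who controls what.**

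| Step | Controlled by | Section |
|---|---|---|
| Overnight fast; confirming start glucose of 70-100 mg/dL | Tester | Execution plan |
| Eating the meal, adding the product | Tester | Execution plan |
| Food and exercise in the two hours after | Tester | Execution plan |
| Logging the start time, which annotates the sensor trace | Tester | Execution plan; iAUC Calculation |
| Mood, feedback, testimonials | Tester | Data Collection; Background |
| Glucose values, every 15 minutes | Sensor | Design |
| Excluding tests started far above the 1-4 AM baseline | Investigators | Test Validation Methods |
| iAUC, peak, time to peak | CRO team, then verified by a practitioner and a statistician | iAUC Calculation |

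**4. Would the existing checks catch differential conduct?** The baseline rule looks only at the starting glucose. It would not reveal an unfinished portion, a shifted log time, or more non-strenuous activity after the Day 3 meal. The sensor records faithfully, but it records whatever the tester did.

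**5. Scale, as illustration only.** Let s be the share of testers with a tie, and b the extra Day 3 fall in iAUC caused by their conduct rather than the product, as a percentage of control iAUC. The shift in the mean effect is s × b. Neither input is in the protocol; both are assumed.

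- s = 0: shift = 0.
- s = 10% (5 of 50), b = 10%: 0.10 × 0.10 = 1 percentage point.
- s = 30% (15 of 50), b = 30%: 0.30 × 0.30 = 9 percentage points.

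Sample size does not enter the formula, so recruiting more testers at the same s would not shrink the shift.

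**The case against.** A reader might infer that ambassadors serve as testers. The protocol does not say so. Recruiting *via* a network may mean only that ambassadors refer others, in which case the proposed rule would describe what already happens. Nor does anything show that an ambassador is paid or has an interest in this product; the network is the CRO's, not the sponsor's. This stands: tied testers are permitted, not shown.

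A reader might also infer that the unblinded tester determines every step behind the outcome. That is wrong, as the table shows. Tester discretion is further narrowed by shipped standardized portions, a 10-minute limit for eating, the fast, the two-hour restrictions and the request to keep the context the same across tests. All of these rely on self-managed compliance, but they are real constraints.

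Three further points have weight. The pre-screener's content is not available, so it may already ask about ties; even so, the protocol has no criterion under which an answer would exclude anyone. The general disclosure duty means that conflicts are not wholly ignored. And favourable conduct on a known product day can come from any tester in an open-label, fixed-order study; excluding tied people leaves that bias in place.

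Finally, the protocol itself advises against final conclusions and disclaims formal research significance. That tempers the claims but does not remove a bias, and the testimonial and marketing uses remain.

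**Conclusion.** The point holds in a limited form. As written, the criteria let people with a commercial tie to the CRO or sponsor be testers in a study where the tester knows the condition and controls intake, product use, conduct around the meal and the logged start time. The general duty to disclose and manage conflicts does not close this gap, because it is not an eligibility rule.

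The size of any resulting bias is unknown. The range of 0 to 9 percentage points of control iAUC only multiplies assumed inputs. It should not be read as an estimate, nor set against the reduction of up to 40% claimed for the ingredient.

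This is an avoidable weakness that is worth closing because doing so is cheap. It does not by itself invalidate the comparison. Eligibility belongs in the protocol, so the gap cannot be left to a statistical analysis plan.

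**What to change.** - Add to the exclusion criteria: current ambassadors, employees, contractors and paid promoters of the CRO or sponsor, and members of their households.
- Define ambassador under Participants enrollment, and state that ambassadors may refer others but not be testers.
- Make sure the online pre-screener asks about such ties, adding a question if it does not already have one.
- If any tied testers are already enrolled, report the Day 2 versus Day 3 comparison and the testimonials with and without them.

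The cost is one criterion, one definition and at most one question, with a slightly smaller recruitment pool. The remaining expectation bias from the open-label, fixed-order design should still be acknowledged when results are reported.

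### The exclusion names medications but not supplements, so the control meal and the off-product days are not assured to be free of mulberry leaf or similar products

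*Protocol*

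**What the plan says.** **Eligibility.** The exclusion list in the Protocol (Inclusion & Exclusion criteria) has one item on other products: "Taking medications that modulate blood glucose response or control blood pressure other than Metformin". It covers two classes of medication and allows metformin. No item mentions supplements, herbal products or teas.

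**Product.** The Summary describes GlucoTrojan as "a powdered supplement sachet containing Reducose, a natural water extract of White Mulberry Leaf". The Rationale adds that "Mulberry leaf extracts are widely consumed in Asia for normalizing post-prandial blood glucose".

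**Contrast.** The Study Objective compares the test meal taken with GlucoTrojan against the same meal alone. The control is a single occasion in the Execution plan: "Day 2: Consume 1 serving of Test Meal for breakfast". Day 3 repeats the meal with the product. Days 4-8 are on product with usual meals. Days 9-13 are off product, in everyday life.

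**Instructions.** Under Design, "The participants are instructed not to make changes in their usual diet and physical exercise during the study period", and "participants are asked to note any medications or activities that can impact their postprandial glucose readings". The Execution plan adds:
- water only from 10 PM to 6 AM before the two test meals;
- no other foods for two hours after the meal;
- a consistent context across experiments, with coffee or tea given as the example;
- logging of events outside the instructed ones.

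**The concern.** A comparison of a meal with mulberry extract against the meal alone needs a control meal without mulberry extract or anything that acts like it. The protocol recognises that such extracts are taken for the very response being measured. Its rule on other products nevertheless stops at medications, a class to which its own product does not belong.

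If a regular user enrols and takes their own product with both test meals, the Day 2 control is already partly treated and the Day 3 minus Day 2 difference shrinks. The same applies to any comparison of Days 4-8 with Days 9-13. If use differs between the two test days, the difference for that tester can move either way: use on Day 2 only understates the product, and use on Day 3 only flatters it.

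**Working it through.** The protocol states no effect size, SD or power for its 50 testers, so there is no figure of its own to reproduce. The check is mainly a reading of the text, followed by an illustration of size.

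**Step 1: does any existing rule keep such a product away from the control meal or Days 9-13?**

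| Provision (Protocol) | What it does | What it leaves open |
|---|---|---|
| Exclusion list | Removes users of glucose-modulating or blood-pressure medications, metformin aside | Users of supplements and teas |
| Overnight fast | Water only until 6 AM | What is taken with breakfast |
| Two-hour rule | No other foods after the meal | Supplements are not named |
| Consistency rule | Same context in every experiment; tea accepted if consistent, type not restricted | Keeps background use equal on both days, so the control stays treated |
| Notes and food log | Record medications, activities and events outside the instructions | Recording does not remove the exposure |
| Usual-diet instruction | Asks for no change of habits | A habitual user has no reason to stop |
| Days 9-13 | Everyday life with meal logging | No restriction on such products |

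None of these closes the gap. A further point concerns Days 9-13. The schedule uses 1 sachet on Day 3 and 5 x 2 = 10 on Days 4-8, 11 in all. The test box holds 15, so 15 - 11 = 4 remain with the tester, and no line says that they are not to be used on Days 9-13.

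**Step 2: how large could the dilution be?** Let p be the share of testers who take an active product with both test meals, and m the fraction of the GlucoTrojan response that it masks. The mean effect is then

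observed effect = true effect x (1 - p x m).

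Neither p nor m is in the documents. With full masking (m = 1, the extreme case):

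| p | Testers of 50 | Assumed 20% reduction reads as | Assumed 40% reduction reads as |
|---|---|---|---|
| 10% | 5 | 18% | 36% |
| 20% | 10 | 16% | 32% |
| 30% | 15 | 14% | 28% |

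The 20% is an assumption. The 40% is the upper figure that the protocol gives for Reducose. With half masking (m = 0.5) at p = 20%, the 20% reduction reads as 20% x (1 - 0.2 x 0.5) = 18%.

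**Step 3: what might that do to power?** For a paired comparison of 50 testers at two-sided 5%, with standardised mean difference dz, full masking and an unchanged SD of the differences,

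power = Phi(dz x (1 - p) x sqrt(50) - 1.96).

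| Assumed dz | p = 0 | 10% | 20% | 30% |
|---|---|---|---|---|
| 0.3 | 56% | 48% | 40% | 32% |
| 0.4 | 81% | 72% | 62% | 51% |
| 0.5 | 94% | 89% | 81% | 70% |

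For example, at dz = 0.4 and p = 0.2: 0.4 x 0.8 x 7.071 - 1.96 = 0.303, and Phi(0.303) = 62%.

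**The case against.** The case on the other side has real weight.

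**Prevalence.** A reader might infer that many testers already use mulberry leaf. The documents do not support that. The Rationale's remark describes Asia. The Background phrase "targeting consumers who follow carbohydrate-heavy Asian diets" describes the product's market, and the exclusion list has no diet criterion. On recruitment the protocol says only "A total of 50 individuals will be recruited via the Tastermonial database and ambassador network", and nothing about what those people take. So one cannot say that the control meal is contaminated, only that it is not assured to be clean. This stands and limits the point.

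**The usual-diet instruction.** A reader might also infer that it tells testers to keep taking a supplement on Day 2. That over-reads it. The Day 2 breakfast is a supplied, standardised meal with its own rules, and the objective defines the control as the meal by itself. A careful tester could well take nothing else with it. Still, no line says so, and the instruction gives a habitual user no signal to stop.

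**Safeguards.** The consistency rule works against use on one test day only, so bias in either direction on Day 2 versus Day 3 presupposes that the rule is not followed. The food log should capture use, which could then be handled in the analysis. Both are partial: the first preserves regular use in both arms, and the second removes none.

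**Direction and comparator.** For regular users the bias is toward no effect, so it would not manufacture a positive claim. Days 9-13 are not the comparator in the stated objective, and they are everyday life by design.

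**Unseen material.** The pre-screener (Appendix III) and the onboarding guide are not shown and may deal with supplements. The listed criteria would still give no specific ground to exclude on the answer.

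**Conclusion.** The point holds as a gap in the eligibility and instruction wording. Users of mulberry leaf or similar supplements or teas can enrol, and nothing that is shown keeps those products away from the Day 2 control meal or Days 9-13. The existing rules protect the test meals in part and Days 9-13 less.

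The size is unknown, because it depends on a prevalence that the documents do not give. The tabulated dilution assumes full masking and regular use with both meals, so it is an upper case for each p. At p = 10% the loss is modest (20% to 18%). It becomes material for a study of 50 only if use is common. The gap does not show that any result would be invalid. It is a cheap improvement to make before recruitment, and it belongs in the protocol because it decides who enrols and what testers take.

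**What to change.** 1. **Exclusion list:** extend the medication item to current use of mulberry leaf (extract or tea), any Reducose product, or another product sold to lower post-meal glucose. Any look-back window is for the investigators to set, as the documents give no basis for a particular length.
2. **Pre-screener:** add a matching question, so that the criterion can be applied.
3. **Instructions for Days 1-14:** state that no such product is used other than the supplied GlucoTrojan on its scheduled days. This also covers the 4 surplus sachets. State that the line overrides the usual-diet instruction under Design.
4. **App:** name supplements and teas beside medications and activities in what testers record, so that any use is visible to the analysis.

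The cost is one eligibility phrase, one screening question, one instruction line and one logging item. A few candidates would be lost, and Days 9-13 would be slightly less representative of everyday life for anyone who would otherwise have used such a product.
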